1 INDICATIONS AND USAGE

1.1 Hypertension

NORVASC® is indicated for the treatment of hypertension, to lower blood pressure. Lowering blood pressure reduces the risk of fatal and nonfatal cardiovascular events, primarily strokes and myocardial infarctions. These benefits have been seen in controlled trials of antihypertensive drugs from a wide variety of pharmacologic classes including NORVASC.

Control of high blood pressure should be part of comprehensive cardiovascular risk management, including, as appropriate, lipid control, diabetes management, antithrombotic therapy, smoking cessation, exercise, and limited sodium intake. Many patients will require more than one drug to achieve blood pressure goals. For specific advice on goals and management, see published guidelines, such as those of the National High Blood Pressure Education Program's Joint National Committee on Prevention, Detection, Evaluation, and Treatment of High Blood Pressure (JNC).

Numerous antihypertensive drugs, from a variety of pharmacologic classes and with different mechanisms of action, have been shown in randomized controlled trials to reduce cardiovascular morbidity and mortality, and it can be concluded that it is blood pressure reduction, and not some other pharmacologic property of the drugs, that is largely responsible for those benefits. The largest and most consistent cardiovascular outcome benefit has been a reduction in the risk of stroke, but reductions in myocardial infarction and cardiovascular mortality also have been seen regularly.

Elevated systolic or diastolic pressure causes increased cardiovascular risk, and the absolute risk increase per mmHg is greater at higher blood pressures, so that even modest reductions of severe hypertension can provide substantial benefit. Relative risk reduction from blood pressure reduction is similar across populations with varying absolute risk, so the absolute benefit is greater in patients who are at higher risk independent of their hypertension (for example, patients with diabetes or hyperlipidemia), and such patients would be expected to benefit from more aggressive treatment to a lower blood pressure goal.

Some antihypertensive drugs have smaller blood pressure effects (as monotherapy) in black patients, and many antihypertensive drugs have additional approved indications and effects (e.g., on angina, heart failure, or diabetic kidney disease). These considerations may guide selection of therapy.

NORVASC may be used alone or in combination with other antihypertensive agents.

1.2 Coronary Artery Disease (CAD)

Chronic Stable Angina

NORVASC is indicated for the symptomatic treatment of chronic stable angina. NORVASC may be used alone or in combination with other antianginal agents.

Vasospastic Angina (Prinzmetal's or Variant Angina)

NORVASC is indicated for the treatment of confirmed or suspected vasospastic angina. NORVASC may be used as monotherapy or in combination with other antianginal agents.

Angiographically Documented CAD

In patients with recently documented CAD by angiography and without heart failure or an ejection fraction <40%, NORVASC is indicated to reduce the risk of hospitalization for angina and to reduce the risk of a coronary revascularization procedure.

2 DOSAGE AND ADMINISTRATION

2.1 Adults

The usual initial antihypertensive oral dose of NORVASC is 5 mg once daily, and the maximum dose is 10 mg once daily.

Small, fragile, or elderly patients, or patients with hepatic insufficiency may be started on 2.5 mg once daily and this dose may be used when adding NORVASC to other antihypertensive therapy.

Adjust dosage according to blood pressure goals. In general, wait 7 to 14 days between titration steps. Titrate more rapidly, however, if clinically warranted, provided the patient is assessed frequently.

Angina: The recommended dose for chronic stable or vasospastic angina is 5–10 mg, with the lower dose suggested in the elderly and in patients with hepatic insufficiency. Most patients will require 10 mg for adequate effect.

Coronary artery disease: The recommended dose range for patients with coronary artery disease is 5–10 mg once daily. In clinical studies, the majority of patients required 10 mg [see *Clinical Studies (14.4)*].

2.2 Children

The effective antihypertensive oral dose in pediatric patients ages 6–17 years is 2.5 mg to 5 mg once daily. Doses in excess of 5 mg daily have not been studied in pediatric patients [see *Clinical Pharmacology (12.4)*, *Clinical Studies (14.1)*].

3 DOSAGE FORMS AND STRENGTHS

Tablets: 2.5 mg white, diamond, flat-faced, beveled edged, with “NORVASC” on one side and “2.5” on the other

Tablets: 5 mg white, elongated octagon, flat-faced, beveled edged, with “NORVASC” on one side and “5” on the other

Tablets: 10 mg white, round, flat-faced, beveled edge, with “NORVASC” on one side and “10” on the other

4 CONTRAINDICATIONS

NORVASC is contraindicated in patients with known sensitivity to amlodipine.

5 WARNINGS AND PRECAUTIONS

5.1 Hypotension

Symptomatic hypotension is possible, particularly in patients with severe aortic stenosis. Because of the gradual onset of action, acute hypotension is unlikely.

5.2 Increased Angina or Myocardial Infarction

Worsening angina and acute myocardial infarction can develop after starting or increasing the dose of NORVASC, particularly in patients with severe obstructive coronary artery disease.

5.3 Patients with Hepatic Failure

Because NORVASC is extensively metabolized by the liver and the plasma elimination half-life ($t_{1/2}$) is 56 hours in patients with impaired hepatic function, titrate slowly when administering NORVASC to patients with severe hepatic impairment.

6 ADVERSE REACTIONS

6.1 Clinical Trials Experience

Because clinical trials are conducted under widely varying conditions, adverse reaction rates observed in the clinical trials of a drug cannot be directly compared to rates in the clinical trials of another drug and may not reflect the rates observed in practice.

NORVASC has been evaluated for safety in more than 11,000 patients in U.S. and foreign clinical trials. In general, treatment with NORVASC was well-tolerated at doses up to 10 mg daily. Most adverse reactions reported during therapy with NORVASC were of mild or moderate severity. In controlled clinical trials directly comparing NORVASC (N=1730) at doses up to 10 mg to placebo (N=1250), discontinuation of NORVASC because of adverse reactions was required in only about 1.5% of patients and was not significantly different from placebo (about 1%). The most commonly reported side effects more frequent than placebo are reflected in the table below. The incidence (%) of side effects that occurred in a dose related manner are as follows:

	2.5 mg N=275	Amlodipine 5 mg N=296	10 mg N=268	Placebo N=520
Edema	1.8	3.0	10.8	0.6
Dizziness	1.1	3.4	3.4	1.5
Flushing	0.7	1.4	2.6	0.0
Palpitation	0.7	1.4	4.5	0.6

Other adverse reactions that were not clearly dose related but were reported with an incidence greater than 1.0% in placebo-controlled clinical trials include the following:

	NORVASC (%) (N=1730)	Placebo (%) (N=1250)
Fatigue	4.5	2.8
Nausea	2.9	1.9
Abdominal Pain	1.6	0.3
Somnolence	1.4	0.6

For several adverse experiences that appear to be drug and dose related, there was a greater incidence in women than men associated with amlodipine treatment as shown in the following table:

	NORVASC		Placebo	
	Male=% (N=1218)	Female=% (N=512)	Male=% (N=914)	Female=% (N=336)
Edema	5.6	14.6	1.4	5.1
Flushing	1.5	4.5	0.3	0.9
Palpitations	1.4	3.3	0.9	0.9
Somnolence	1.3	1.6	0.8	0.3

The following events occurred in <1% but >0.1% of patients in controlled clinical trials or under conditions of open trials or marketing experience where a causal relationship is uncertain; they are listed to alert the physician to a possible relationship:

Cardiovascular: arrhythmia (including ventricular tachycardia and atrial fibrillation), bradycardia, chest pain, peripheral ischemia, syncope, tachycardia, vasculitis.

Central and Peripheral Nervous System: hypoesthesia, neuropathy peripheral, paresthesia, tremor, vertigo.

Gastrointestinal: anorexia, constipation, dysphagia, diarrhea, flatulence, pancreatitis, vomiting, gingival hyperplasia.

General: allergic reaction, asthenia,¹ back pain, hot flushes, malaise, pain, rigors, weight gain, weight decrease.

Musculoskeletal System: arthralgia, arthrosis, muscle cramps,¹ myalgia.

Psychiatric: sexual dysfunction (male¹ and female), insomnia, nervousness, depression, abnormal dreams, anxiety, depersonalization.

Respiratory System: dyspnea,¹ epistaxis.

Skin and Appendages: angioedema, erythema multiforme, pruritus,¹ rash,¹ rash erythematous, rash maculopapular.

Special Senses: abnormal vision, conjunctivitis, diplopia, eye pain, tinnitus.

Urinary System: micturition frequency, micturition disorder, nocturia.

Autonomic Nervous System: dry mouth, sweating increased.

Metabolic and Nutritional: hyperglycemia, thirst.

Hemopoietic: leukopenia, purpura, thrombocytopenia.

¹ These events occurred in less than 1% in placebo-controlled trials, but the incidence of these side effects was between 1% and 2% in all multiple dose studies.

NORVASC therapy has not been associated with clinically significant changes in routine laboratory tests. No clinically relevant changes were noted in serum potassium, serum glucose, total triglycerides, total cholesterol, HDL cholesterol, uric acid, blood urea nitrogen, or creatinine.

In the CAMELOT and PREVENT studies [see *Clinical Studies (14.4)*], the adverse event profile was similar to that reported previously (see above), with the most common adverse event being peripheral edema.

6.2 Postmarketing Experience

Because these reactions are reported voluntarily from a population of uncertain size, it is not always possible to reliably estimate their frequency or establish a causal relationship to drug exposure.

The following postmarketing event has been reported infrequently where a causal relationship is uncertain: gynecomastia. In postmarketing experience, jaundice and hepatic enzyme elevations (mostly consistent with cholestasis or hepatitis), in some cases severe enough to require hospitalization, have been reported in association with use of amlodipine.

Postmarketing reporting has also revealed a possible association between extrapyramidal disorder and amlodipine.

NORVASC has been used safely in patients with chronic obstructive pulmonary disease, well-compensated congestive heart failure, coronary artery disease, peripheral vascular disease, diabetes mellitus, and abnormal lipid profiles.

7 DRUG INTERACTIONS

7.1 Impact of Other Drugs on Amlodipine

CYP3A Inhibitors

Co-administration with CYP3A inhibitors (moderate and strong) results in increased systemic exposure to amlodipine and may require dose reduction. Monitor for symptoms of hypotension and edema when amlodipine is co-administered with CYP3A inhibitors to determine the need for dose adjustment [see *Clinical Pharmacology (12.3)*].

CYP3A Inducers

No information is available on the quantitative effects of CYP3A inducers on amlodipine. Blood pressure should be closely monitored when amlodipine is co-administered with CYP3A inducers.

Sildenafil

Monitor for hypotension when sildenafil is co-administered with amlodipine [see *Clinical Pharmacology (12.2)*].

7.2 Impact of Amlodipine on Other Drugs

Simvastatin

Co-administration of simvastatin with amlodipine increases the systemic exposure of simvastatin. Limit the dose of simvastatin in patients on amlodipine to 20 mg daily [see *Clinical Pharmacology (12.3)*].

Immunosuppressants

Amlodipine may increase the systemic exposure of cyclosporine or tacrolimus when co-administered. Frequent monitoring of trough blood levels of cyclosporine and tacrolimus is recommended and adjust the dose when appropriate [see *Clinical Pharmacology (12.3)*].

8 USE IN SPECIFIC POPULATIONS

8.1 Pregnancy

Pregnancy Category C

There are no adequate and well-controlled studies in pregnant women. Amlodipine should be used during pregnancy only if the potential benefit justifies the risk to the fetus.

No evidence of teratogenicity or other embryo/fetal toxicity was found when pregnant rats and rabbits were treated orally with amlodipine maleate at doses up to 10 mg amlodipine/kg/day (respectively, 8 times² and 23 times² the maximum recommended human dose of 10 mg on a mg/m² basis) during their respective periods of major organogenesis. However, litter size was significantly decreased (by about 50%) and the number of intrauterine deaths was significantly increased (about 5-fold) in rats receiving amlodipine maleate at a dose equivalent to 10 mg amlodipine/kg/day for 14 days before mating and throughout mating and gestation. Amlodipine maleate has been shown to prolong both the gestation period and the duration of labor in rats at this dose.

² Based on patient weight of 50 kg.

8.3 Nursing Mothers

It is not known whether amlodipine is excreted in human milk. In the absence of this information, it is recommended that nursing be discontinued while NORVASC is administered.

8.4 Pediatric Use

NORVASC (2.5 to 5 mg daily) is effective in lowering blood pressure in patients 6 to 17 years [see *Clinical Studies (14.1)*]. Effect of NORVASC on blood pressure in patients less than 6 years of age is not known.

8.5 Geriatric Use

Clinical studies of NORVASC did not include sufficient numbers of subjects aged 65 and over to determine whether they respond differently from younger subjects. Other reported clinical experience has not identified differences in responses between the elderly and younger patients. In general, dose selection for an elderly patient should be cautious, usually starting at the low end of the dosing range, reflecting the greater frequency of decreased hepatic, renal, or cardiac function, and of concomitant disease or other drug therapy. Elderly patients have decreased clearance of amlodipine with a resulting increase of AUC of approximately 40–60%, and a lower initial dose may be required [see *Dosage and Administration (2.1)*].

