4. ELIGIBILITY CRITERIA

4.1 Inclusion Criteria

A subject may be included in this study if he or she meets all of the following criteria:

1. Adult 40 to 75 years of age;
2. Existing hypertension that is being treated using pharmacological therapy with a single agent that is not a calcium channel blocker;
3. $SBP_{day} > 135$ and ≤ 169 mmHg and $DBP_{day} \leq 110$ mmHg at Day 0 (i.e., after the 10- to 14-day washout from prior BP medication);
4. Body Mass Index (BMI) of 18.5 to 34.9 kg/m²;
5. Healthy (other than hypertension) as determined by the Investigator based on medical history, physical examination, vital signs, 12-lead ECG, and clinical laboratory tests;
6. A negative pregnancy test at initial screening visit;
7. If WCBP, agree to use a highly effective form of birth control while on study (from Screening through final study visit);

Highly effective methods of birth control are defined as those, alone or in combination, that result in a low failure rate (i.e., less than 1% per year) when used consistently and correctly. Forms of birth control include intrauterine device (IUD), birth control patch or vaginal ring, oral, or injectable or implanted contraceptives, or a vasectomized partner, or abstinence from sexual intercourse. Abstinence is acceptable only as true abstinence: when this is in line with the preferred and usual lifestyle of the subject. Periodic abstinence (e.g., calendar, ovulation, symptothermal, post-ovulation methods) and withdrawal are not acceptable methods of contraception.

A woman that is postmenopausal (≥ 2 years since last menstrual period) or permanently sterilized (e.g. tubal occlusion, hysterectomy, bilateral salpingectomy) is not considered a WCBP.

8. Able to comprehend and sign an ICF.

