10.3 Statistical Analysis of Pharmacokinetic Data

Subjects will have a blood sample drawn on Day 14, approximately 24 hours after receiving the final dose of study drugs, for the measurement of amlodipine concentration. Only subjects enrolled at Investigational Sites that have UV-shielded lights will participate in the PK blood collection. Due to the design of the trial (randomized, double-blind, placebo-controlled), this blood sample will be collected and analyzed for all participating subjects, regardless of whether they are in a treatment arm that receives amlodipine.

The plasma concentration of amlodipine will be determined by validated LC-MS/MS method. All plasma concentration values below the lower limit of quantification (LLOQ) will be reported as zero. Individual amlodipine plasma concentration data will be listed.

A t-test will compare the plasma concentration of amlodipine in those subjects who receive amlodipine tablets (10 mg) given alone (with matched celecoxib placebo) (arm 2) with those who receive amlodipine tablets (10 mg) and celecoxib capsules (200 mg) given together (arm 1).

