### 7.2. Covariates and Subgroups

All ANCOVA models will include the baseline value of the variable as a covariate and treatment group as fixed effect with no interaction term.

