### Pharmacokinetics

For the individual patient data listing of amlodipine plasma concentrations, all values below the LLOQ will be reported as BLQ, as in the bioanalytical report.

Non-transformed amlodipine plasma concentration values at Day 14 will be summarized for the PK population by treatment group by descriptive statistics (n, mean, SD, median, and range). A t-test will compare the non-transformed amlodipine plasma concentration values in those subjects who receive amlodipine tablets (10 mg) given alone (with matched celecoxib placebo) (arm 2) with those who receive amlodipine tablets (10 mg) and celecoxib capsules (200 mg) given together (arm 1). A box plot of the non-transformed amlodipine plasma concentrations at Day 14 by treatment arm will be produced. For these analyses, BLQ values will be treated as 0, and only treatment arms that included amlodipine will be included (i.e., the placebo + placebo arm will not be included).

Log-transformed amlodipine plasma concentration values at Day 14 will be summarized for the PK population by treatment group by descriptive statistics (n, mean, SD, median, and range). A t-test will compare the log-transformed amlodipine plasma concentration values in those subjects who receive amlodipine tablets (10 mg) given alone (with matched celecoxib placebo) (arm 2) with those who receive amlodipine tablets (10 mg) and celecoxib capsules (200 mg) given together (arm 1). For these analyses, only treatment arms that included amlodipine will be included (i.e., the placebo + placebo arm will not be included). Further, all BLQ values will be treated as 0.04 ng/mL rather than 0. Zero cannot be log-transformed. Assignment of the BLQ values to a nonzero number will allow computation of the log transformation. The selection of 0.04 ng/mL as the nonzero number for BLQ assignment was based on the LLOQ of the validated bioanalytical method (i.e., 0.05 ng/mL) and selecting the next lowest number at the hundredth decimal place.

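### The Day 14 amlodipine comparison ignores age, a known determinant of amlodipine exposure; the test is valid but less precise than it could be, and an age-adjusted model should be added beside it.

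*Protocol*

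**What the plan says.** Protocol 2.2 lists the effect of celecoxib on amlodipine concentration as the third secondary objective, outside the four-step efficacy hierarchy. For the single sample taken about 24 hours after the last dose, protocol 10.3 states: "A t-test will compare the plasma concentration of amlodipine in those subjects who receive amlodipine tablets (10 mg) given alone" with those given the combination.

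SAP 7.10 (Pharmacokinetics) keeps that test on the raw scale: "A t-test will compare the non-transformed amlodipine plasma concentration values in those subjects who receive amlodipine tablets (10 mg) given alone". It adds a log-scale version: "A t-test will compare the log-transformed amlodipine plasma concentration values in those subjects who receive amlodipine tablets (10 mg) given alone". None of the three statements names a covariate. Where the SAP does adjust, in section 7.2, it uses the baseline value of the outcome and not age: "All ANCOVA models will include the baseline value of the variable as a covariate and treatment group as fixed effect with no interaction term".

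Protocol 4.1 admits "Adult 40 to 75 years of age". The amlodipine label in protocol Appendix F, section 8.5 (Geriatric Use), says: "Elderly patients have decreased clearance of amlodipine with a resulting increase of AUC of approximately 40–60" per cent. Section 12.3 of the same label repeats the figure.

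Under SAP 4.1 the PK population is limited to sites with UV-shielded lights and to subjects with a Day 14 sample in the 24 ± 1 hour window. Its size is not given. SAP 7.5 tabulates age by arm for the Safety population, and SAP 7.10 adds a table by site. Neither is for the PK population.

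**The concern.** The sponsor's own appended label names a determinant of amlodipine exposure about as large as the effect under test. Protocol section 1 reports that celecoxib lowered amlodipine levels by about a third in study KIT-302-03-01, a log effect of ln 1.5 = 0.405. The label's age contrast is ln 1.4 to ln 1.6, or 0.336 to 0.470. With ages from 40 to 75 enrolled and no age term in the model, that variation goes into the error term.

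No baseline concentration is available as a covariate, because protocol 4.2 excludes anyone who has ever taken a calcium channel blocker. Age is the documented alternative and is already recorded. What is at stake is the width of the interval around the celecoxib effect, and power if few sites contribute samples.

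**Working it through.** The documents state no PK sample size, power, SD or CV, so there is no plan figure to reproduce.

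**Inputs from the documents**
- Effect sought: a one-third fall, d = −ln(2/3) = 0.405 (protocol section 1).
- Age effect: AUC ratio r = 1.4 to 1.6 (Appendix F label).
- Arms 1 and 2 in a 1:1 ratio, under the planned 3:3:1 and the achieved 6:6:1 (SAP 3.2).
- Planned arm size: 105 × 3/7 = 45. This is about the most that the PK comparison could have under the plan.

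**Assumptions not in the documents**
- Within-age CV 30 to 60 per cent.
- Share of elderly p = 20 to 50 per cent.
- n = 15, 25 or 45 per arm.
- The AUC ratio carries over to the 24-hour concentration.
- Two-sided 5 per cent level. The SAP sets this for safety tests (7.3) and gives no level for PK.

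**Precision.** Within-age log variance is ln(1 + CV²). Age adds p(1 − p)(ln r)². The ratio of unadjusted to adjusted SE is the square root of (within + age)/within.

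| CV | p | r | Within | Age | Age share | SE ratio | SE cut |
|---|---|---|---|---|---|---|---|
| 60% | 20% | 1.4 | 0.307 | 0.018 | 6% | 1.03 | 3% |
| 40% | 30% | 1.6 | 0.148 | 0.046 | 24% | 1.15 | 13% |
| 30% | 50% | 1.6 | 0.086 | 0.055 | 39% | 1.28 | 22% |

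The first and last rows are the extremes of the assumed range.

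**Power, middle row.** By the normal approximation, power is Φ(0.405/(SD√(2/n)) − 1.96). The SD is √0.195 = 0.441 unadjusted and √0.148 = 0.385 adjusted.

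| n per arm | Unadjusted | Age effect fully removed |
|---|---|---|
| 15 | 71% | 82% |
| 25 | 90% | 96% |
| 45 | 99.2% | 99.9% |

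For 80 per cent power, 19 per arm are needed unadjusted and 15 adjusted. Simulating the unadjusted t-test itself gave 68, 89 and 99 per cent, so the approximation is slightly generous at n = 15.

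**A linear age term against a two-level step.** Full removal is the best case. If age acted as an elderly/younger step and ages were uniform (assumption), a linear term would capture 3p(1 − p) of the step's variance, which is 63 per cent at p = 30 per cent. The residual variance in the middle row becomes 0.1484 + 0.37 × 0.0464 = 0.1656. The SE cut falls from 13 to 8 per cent, and power becomes 78, 94 and 99.7 per cent.

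**Validity.** In 50,000 simulated null trials at each n (p = 30 per cent, r = 1.6, CV 40 per cent), the unadjusted t-test rejected in 4.9 to 5.1 per cent on the log scale and 4.8 to 4.9 per cent on the raw scale.

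**Chance imbalance.** The difference between arms in the share of elderly has SD √(2p(1 − p)/n). At p = 50 per cent this is 0.183 for n = 15 and 0.105 for n = 45. With r = 1.6, the central 95 per cent of shifts in the geometric mean ratio, exp(±1.96 × SD × ln 1.6), is −15 to +18 per cent and −9 to +10 per cent. For age alone to produce a ratio of two-thirds, the arms would have to differ by 0.405/0.470 = 86 percentage points at r = 1.6. At r = 1.4 the figure is 0.405/0.336 = 121 points, which is impossible.

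**The case against.** A reader might infer that leaving age out biases the comparison, or leaves an imbalance uncorrected. The documents do not support that. Arms 1 and 2 are randomised, double blind and 1:1 under both allocations, so no age imbalance is expected. Chance imbalance is already reflected in the t-test's standard error, and the simulated type I error is about 5 per cent. A realised imbalance in a small PK subset could shift the point estimate, but it could not plausibly create a one-third fall.

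A reader might also take the PK subset to be small, or the test to be underpowered. Neither is stated. The prior study also sampled only a subset, drawn from amlodipine arms of about 46 each (152 × 1.5/5), and reported p < 0.001.

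The label figure may not carry over. It describes elderly patients and does not isolate age. It concerns AUC, whereas the trial measures one 24-hour level. The trial also requires subjects to be healthy apart from hypertension, caps age at 75, and excludes other current cardiovascular disease, Child-Pugh class B or C cirrhosis and creatinine clearance below 50 ml/min. The effect here could be smaller.

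Timing counts too. SAP 1.5 dates v4.0 to April 20, 2018, after unblinding, and SAP 1.3.10 cites a bioanalytical report amendment of March 22, 2018. Replacing the protocol's test with a newly chosen covariate model at that stage would look data-dependent.

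All of this stands. It limits the size of the point and the form of the remedy. It does not remove the case for an age-adjusted estimate, because age is a documented determinant of exposure, is already collected, and has no baseline concentration to stand in for it. The site-by-arm age tables help in judging balance but are not restricted to subjects in the PK analysis.

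**Conclusion.** The point holds as a loss of precision in a valid, unbiased test. Nothing in the label is an error; the omission lies in protocol 10.3 and SAP 7.10.

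Over the assumed ranges the best-case reduction in SE is about 3 to 22 per cent, and less if a linear age term captures only part of the effect. In the middle example this is worth up to 11 points of power at 15 per arm and 6 at 25. It is worth less than one point at 45. Which case applies cannot be settled from the documents, because PK numbers, variability and age mix are not given. This is a minor but specific improvement to a secondary analysis outside the gatekeeping hierarchy.

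**What to change.** In SAP 7.10 (Pharmacokinetics), add a linear model of log amlodipine concentration on arm (1 against 2) and age in years as a continuous covariate. Report the geometric mean ratio with its 95% CI beside the t-tests already specified. Keep the protocol's t-test in its present role; the model supplements it and does not replace it.

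Label the model as an analysis added after unblinding, and list it in SAP 1.3 as a change from the protocol. Tabulate age by arm for the PK population, so that the reader can see the balance in the subjects analysed.

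The cost is one degree of freedom, one extra model and one small table. No new data are needed, since age is already in the CRF.
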